8.3 Definitions of analysis sets

8.3.1 Full analysis set (FAS)

All patients who received at least one dose of either IP will be included in the full analysis set.

8.3.2 Efficacy analysis set (EFR population)

The EFR analysis set will be all patients who have received at least one dose of either IP and have measurable disease at baseline according to the independent review of baseline imaging data.

The primary analysis of ORR, and analyses of DoR and DCR by ICR will be produced based on the EFR analysis set. All other efficacy variables (ORR, DoR, DCR based on investigator assessment; PFS, OS, TDT) and PRO variables will be summarized using the FAS.

Demographic data will be summarized for the FAS and to support the primary analysis, also for the EFR set (if different).

8.3.3 Safety analysis set

This is the same set as the FAS; ie, all patients who received at least one dose of either IP.

8.3.4 PK analysis set

All patients in the FAS providing at least 1 reportable PK concentration.

8.4 Outcome measures for analyses

Independent Central Review of RECIST based assessments

The ICR of all radiological imaging data will be carried out using RECIST version 1.1. All radiological scans for all patients (including those at unscheduled visits, or outside visit windows) will be provided to the ICR. Prior RT reports for patients (at baseline) and information on any lesions that were biopsied to provide a tumor sample for study entry (see Section 5.7.2) will also be provided to allow the selection of appropriate target lesions. The imaging scans will be reviewed by two independent radiologists using RECIST 1.1 criteria and will be adjudicated if required. For each patient, the ICR will define the overall visit response data (CR, PR, SD, PD or not evaluable [NE]) and the relevant scan dates for each time point (ie, for visits where response or progression is/is not identified). If a patient has had a tumor assessment which cannot be evaluated then the patient will be assigned a visit response of NE (unless there is evidence of progression in which case the response will be assigned as PD).

Further details of the ICR will be documented in the Independent Review Charter.

Investigator RECIST based assessments

From the investigators review of the imaging scans, the RECIST tumor response data will be used to determine each patient's visit response according to RECIST version 1.1. At each visit, patients will be programmatically assigned a RECIST 1.1 visit response of CR, PR, SD or PD depending on the status of their disease compared with baseline and previous assessments. If a patient has had a tumor assessment which cannot be evaluated then the patient will be assigned a visit response of NE (unless there is evidence of progression in which case the response will be assigned as PD).

8.4.1 Primary Endpoint

Objective Response Rate (ORR)

ORR is defined as the number (%) of patients with measurable disease at baseline, with at least one visit response of CR or PR that is confirmed at least 4 weeks later. For the primary analysis ICR is required for both the initial response and confirmation. Data obtained up until progression, or last evaluable assessment in the absence of progression, will be included in the assessment of ORR. However, any CR or PR which occurred or was confirmed after a further anticancer therapy was received will not be included in numerator of the ORR calculation. In the case where a patient has two non-consecutive visit responses of PR or CR, then, as long as the time between the 2 visits of PR or CR is greater than 4 weeks and there is no PD between the PR visits, the patient will be defined as a responder. Note that CR followed by PR is classed as progression.

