This appendix details the implementation of Response Evaluation Criteria In Solid Tumours (RECIST) 1.1 guidelines ([Eisenhauer et al 2009](#)) for the D8488C00001 study with regards to the Investigator assessment of tumour burden including protocol-specific requirements for this study.

DEFINITION OF MEASURABLE, NON-MEASURABLE, TARGET AND NON-TARGET LESIONS

Only patients with measurable disease at baseline should be included in the study. Measurable disease is defined by the presence of at least 1 measurable lesion that has not been previously irradiated.

Measurable:

A lesion, not previously irradiated or biopsied per the protocol prior to enrollment/randomisation, that can be accurately measured at baseline as ≥ 10 mm in the longest diameter (except lymph nodes which must have short axis ≥ 15 mm) with computed tomography (CT) or magnetic resonance imaging (MRI) and which is suitable for accurate repeated measurements.

Non-measurable:

- All other lesions, including small lesions (longest diameter < 10 mm or pathological lymph nodes with ≥ 10 mm to < 15 mm short axis at baseline¹).
- Truly non-measurable lesions include the following: bone lesions, leptomeningeal disease, ascites, pleural/pericardial effusion, inflammatory breast disease, lymphangitic involvement of skin or lung, abdominal masses/abdominal organomegaly identified by physical examination that is not measurable by CT or MRI.
- Lesion biopsied per the protocol prior to randomisation
- Previously irradiated lesions²

¹ Nodes with < 10 mm short axis are considered non-pathological and should not be recorded or followed as non-target lesions (NTLs).

² Localised post-radiation changes which affect lesion sizes may occur. Therefore, lesions that have been previously irradiated will not be considered measurable and must be selected as NTL at baseline and followed up as part of the NTL assessment.

- Skin lesions assessed by clinical examination
- Brain metastasis.

Special cases:

- Lytic bone lesions or mixed lytic–blastic lesions, with identifiable soft tissue components, can be considered measurable if the soft tissue component meets the definition of measurability. Blastic lesions are considered non-measurable.
- Cystic metastases can be considered measurable lesions if they meet the criteria for measurability from a radiological point of view, but if non-cystic lesions are present in the same patient; these should be selected as target lesions (TLs).

Target lesions:

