For calculation of PD and PR for TLs percentage changes from baseline and previous minimum should be rounded to 1 d.p. before assigning a TL response. For example 19.95% should be rounded to 20.0% but 19.94% should be rounded to 19.9%

Missing TL data

For a visit to be evaluable then all TL measurements should be recorded. However, a visit response of PD should still be assigned if any of the following occurred

- A new lesion is recorded
- A NTL visit response of PD is recorded
- The sum of TLs is sufficiently increased to result in a 20% increase, and an absolute increase of ≥ 5 mm, from nadir even assuming the non-recorded TLs have disappeared

Note: the nadir can only be taken from assessments where all the TLs had a LD recorded.

If there is at least one TL measurement missing and a visit response of PD cannot be assigned, the visit response is not evaluable (NE).

Lymph nodes

For lymph nodes, if the size reduces to < 10 mm then these are considered non-pathological. However a size will still be given and this size should still be used to determine the TL visit response as normal. In the special case where all lymph nodes are < 10 mm and all other TLs are 0mm then although the sum may be >0 mm the calculation of TL response should be over-written as a CR.

TL visit responses subsequent to CR

A CR can only be followed by CR, PD or NE. If a CR has occurred then the following rules at the subsequent visits must be applied:

- Step 1: If all lesions meet the CR criteria (i.e. 0mm or < 10 mm for lymph nodes) then response will be set to CR irrespective of whether the criteria for PD of TL is also met i.e. if a lymph node LD increases by 20% but remains < 10 mm.
- Step 2: If some lesion measurements are missing but all other lesions meet the CR criteria (i.e. 0mm or < 10 mm for lymph nodes) then response will be set to NE irrespective of whether, when referencing the sum of TL diameters, the criteria for PD are also met.
- Step 3: If not all lesions meet the CR criteria and the sum of lesions meets the criteria for PD then response will be set to PD
- Step 4: If after steps 1 – 3 a response can still not be determined the response will be set to remain as CR

TL too big to measure

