3.1.3 Overall visit response

Table 5 defines how the previously defined TL and NTL visit responses will be combined with new lesion information to give an overall visit response for investigator assessments.

Table 5 Overall visit responses

TARGET	NON-TARGET	NEW LESIONS	OVERALL VISIT RESPONSE
CR	CR or NA	No (or NE)	CR
CR	Non-CR/Non-PD or NE	No (or NE)	PR
PR	Non-PD or NE or NA	No (or NE)	PR
SD	Non-PD or NE or NA	No (or NE)	SD
PD	Any	Any	PD
Any	PD	Any	PD
Any	Any	Yes	PD
NE	Non-PD or NE or NA	No (or NE)	NE

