3.2.1 Primary Endpoint

The primary efficacy endpoint variable is Objective Response Rate (ORR), defined as the percentage of patients with objective response according to RECIST 1.1 by ICR using the evaluable for response analysis set (all patients who have received at least 1 dose of IPs and have measurable disease at baseline according to ICR).

The secondary endpoint variable of ORR using the investigators assessment of RECIST and based on the full analysis set will also be analysed.

An additional sensitivity analysis of ORR will be performed using the ICR data summarized using the full analysis set.

ORR will only include patients whose response has been confirmed by a second scan at least 4 weeks after the initial response. A confirmed response of CR/PR means that a response of CR/PR is recorded at 1 visit and confirmed by repeat imaging not less than 4 weeks after the visit when the response was first observed with no evidence of progression between the initial and CR/PR confirmation visit. Data obtained up until progression, or last evaluable assessment in the absence of progression, will be included in the assessment of ORR. Patients who receive a subsequent anti-cancer therapy (note that for this analysis radiotherapy is not considered a subsequent anti-cancer therapy) and then respond will not be included as responders in the ORR (i.e. both visits contributing to a response must be prior to subsequent therapy for the patient to be considered as a responder).

In the case where a patient has two non-consecutive visit responses of PR, then, as long as the time between the 2 visits of PR is greater than 4 weeks and there is no PD between the PR visits, the patient will be defined as a responder. Similarly, if a patient has visit responses of CR, NE, CR, then, as long as the time between the 2 visits of CR is greater than 4 weeks, then a best response of CR will be assigned.

Table 6 below outlines scenarios for the first and subsequent visit responses and the rules that will be followed to determine whether such patients would be counted in the numerator of ORR for the primary analysis and their classification for Best Objective Response (BOR) for the primary analysis. BOR is included as supportive data for the ORR endpoint.

Table 6 Confirmed ORR and BoR criteria

First time point	Second time point	Confirmed Responder for ORR	Best objective response
CR	CR	Yes	CR
CR	PR	Scenario not possible, CR can only be followed by CR PD, NE	SD, PD or PR ^a

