CR	SD	Scenario not possible, CR can only be followed by CR PD, NE	SD provided minimum criteria for SD duration met, otherwise, PD
CR	PD	No	SD provided minimum criteria for SD duration met, otherwise, PD
CR	NE	No	SD provided minimum criteria for SD duration met, otherwise NE
PR	CR	Yes	PR
PR	PR	Yes	PR
PR	SD	No	SD
PR	PD	No	SD provided minimum criteria for SD duration met, otherwise, PD
PR	NE	No	SD provided minimum criteria for SD duration met, otherwise NE
CR/PR	Second timepoint not reached at time of analysis	No*	SD provided minimum criteria for SD duration met, otherwise NE
CR/PR	Patient withdrew consent before second timepoint reached	No*	SD provided minimum criteria for SD duration met, otherwise NE
NE	NE		NE

CR = complete response, PR = partial response, SD = stable disease, PD = progressive disease, and NE = inevaluable. (Eisenhauer et al 2009).

* Note for the interim analysis, ORR will include both confirmed and unconfirmed responses, so patients in these scenarios would be counted as responders.

^a If a CR is truly met at first time point, then any disease seen at a subsequent time point, even disease meeting PR criteria relative to baseline, makes the disease PD at that point (since disease must have reappeared after CR). Best response would depend on whether minimum duration for SD was met (scan at least 7 weeks post-baseline). However, sometimes 'CR' may be claimed when subsequent scans suggest small lesions were likely still present and in fact the patient had PR, not CR at the first time point. Under these circumstances, the original CR should be changed to PR and the best response is PR.

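### For investigator assessments, a non-evaluable non-target read after a complete response is scored PR, which Protocol 8.4.1 then classes as progression and SAP Table 6 calls impossible

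*Protocol*

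**What the plan says.** **Visit scoring.** SAP 3.1.3, Table 5, combines target, non-target and new-lesion status "to give an overall visit response for investigator assessments". For a target CR, the row covering both persisting and unread non-target disease is "Non-CR/Non-PD or NE No (or NE) PR". Protocol Appendix F, Table 23, uses two separate rows and also gives PR in each. That appendix is written "with regards to the Investigator assessment of tumour burden including protocol-specific requirements for this study".

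**Sequence rule in the protocol.** Section 8.4.1 states "Note that CR followed by PR is classed as progression", whatever the reason for the PR.

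**Sequence rule in the SAP.** For CR then PR, Table 6 (SAP 3.2.1) replaces the yes/no responder status with "Scenario not possible, CR can only be followed by CR PD, NE" and lists three possible best responses: SD, PD or PR. Its footnote a says that after a true CR "any disease seen at a subsequent time point, even disease meeting PR criteria relative to baseline, makes the disease PD at that point". Alternatively, if later scans suggest small lesions had been there all along, the CR is relabelled PR. The underlying rule, "A CR can only be followed by CR, PD or NE", stands in SAP 3.1.1 under the heading on target-lesion responses after CR.

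**Missing reads.** SAP 3.2.1 accepts CR, NE, CR as a best response of CR if the two CR visits are more than 4 weeks apart.

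**Central review.** Under SAP 3.1, ICR readers supply the overall visit response themselves and it is not programmed. The endpoints are then programmed for both ICR and investigator data.

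**The concern.** The note in Protocol 8.4.1 makes sense when tumour that had cleared is seen again. But the scoring tables give the same label, PR, to a visit at which nothing was seen because the non-target lesions could not be evaluated. The note cannot tell the two apart.

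The result is also uneven. Under SAP 3.1.1 and Table 5, an unread target lesion after a CR gives an overall NE, which the CR, NE, CR rule protects. An unread non-target lesion gives PR, which that rule does not protect.

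At stake are investigator-assessed ORR and, if the note is carried further, investigator-assessed PFS and DoR. Any error falls on complete responders and only ever worsens their outcome. The SAP also leaves a reachable sequence without a rule, so in an open-label, single-arm trial a programmer would have to choose one with the data in view.

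**Working it through.** The plan states no figure that depends on this point, so the check is of the rules, followed by a rough size.

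**Step 1. Can CR then PR occur?** Yes. In SAP Table 5, target CR with non-target CR is CR. At the next visit, target CR with non-target NE and no new lesion is PR. The SAP 3.1.1 sequence rule works on target lesions, which remain CR throughout, so it does not block this route. Footnote a to Table 6 needs disease to be seen or to have been present all along, and an unread lesion is neither. Tables 5 and 6 therefore contradict each other.

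**Step 2. What follows?** I applied Table 5 to five sequences (target/non-target status by visit) and required two CR or PR visits before any PD for a confirmed response.

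| Sequence | Visit responses | PR after CR read as PD (8.4.1) | Same visit read as NE |
|---|---|---|---|
| A: CR/CR, CR/NE, CR/CR | CR, PR, CR | not a responder; PD at visit 2 | responder; no PD |
| B: CR/CR, CR/CR, CR/NE, CR/CR | CR, CR, PR, CR | responder; PD at visit 3 | responder; no PD |
| C: PR/persisting, CR/CR, CR/NE, CR/CR | PR, CR, PR, CR | responder; PD at visit 3 | responder; no PD |
| D: PR/persisting, CR/NE | PR, PR | responder; no PD | responder; no PD |
| E: no non-target lesions, CR, CR | CR, CR | responder; no PD | responder; no PD |

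Leaving the visit as PR without the note gives the same results as the NE column. Responder status is lost only in A. In B and C the response is already confirmed, so only PFS and DoR could change.

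**Step 3. Is there a progression date?** Protocol 8.4.2 and SAP 3.2.2 date progression from the component that triggered it. In A, B and C no component did, so the date is undefined.

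**Step 4. Size.** Inputs:
- N = 60 (Protocol 8.2).
- CR rate from 2% (Protocol Table 2, single-agent olaparib) to 5/44 = 11% (Protocol 1.1.4.3, Phase II combination).
- Probability of non-target NE per visit, 3% to 10%. This is assumed; the documents give none.
- Three visits after the CR, also assumed.

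Loss of responder status (NE at the confirming visit) = 60 × CR rate × NE probability:
- low: 60 × 0.02 × 0.03 = 0.04
- high: 60 × 0.11 × 0.10 = 0.66

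Any visit read as progression = 60 × CR rate × (1 − (1 − NE)³):
- low: 60 × 0.02 × (1 − 0.97³) = 0.10
- high: 60 × 0.11 × (1 − 0.90³) = 1.79

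Both are upper bounds for their inputs, because they count patients without non-target lesions and, in the first formula, CRs reached through PR.

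One patient is 1/60 = 1.7 percentage points of ORR. For example, 15/60 is 25.0% (Clopper-Pearson 14.7% to 37.9%) and 14/60 is 23.3% (13.4% to 36.0%).

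**The case against.** The strongest reply is that this is an undefined cell in a table, with consequences that are mostly inferred. Much of that stands.

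- **Primary ORR.** A reader might infer that a patient would drop out of the primary ORR numerator. The documents do not support that. SAP Table 5 and Appendix F are written for investigator data, and ICR readers supply their own visit responses. Protocol 8.4 and SAP 3.2 assign NE to an ICR assessment that cannot be evaluated. How readers score target CR with non-target NE belongs to the Independent Review Charter, which is not among the documents.
- **PFS and DoR.** A reader might infer that the text assigns a false progression date. The note sits in the ORR section, and the PFS definition does not list CR to PR. That definition does include an overall assessment of progression, so carrying the note over is possible but not stated.
- **Decision criterion.** A reader might infer that one lost patient upsets the 90% confidence criterion. With the Beta(1/3, 1/3) prior, P(ORR ≥ 20%) is 0.939 at 17/60 and 0.894 at 16/60. But that is the only adjacent pair at N = 60 that crosses 0.90 (0.827 at 15, 0.967 at 18). The criterion was also set alongside 30/100 and is not restated for 60, and it concerns the ICR analysis.
- **Rates.** The 11% CR rate comes from platinum-sensitive patients, most with one or two prior lines. Non-target NE requires that the investigator cannot give an evaluable overall non-target assessment, so one unimaged area does not automatically qualify.

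The contradiction itself survives. The SAP does not repeat the protocol's note, but it gives no other rule for this sequence, and the protocol's unqualified sentence is still current.

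**Conclusion.** The point holds for investigator assessments. Two current rules, applied together, turn a non-evaluable non-target read after a CR into progression, and the SAP calls the sequence impossible when its own Table 5 generates it. Investigator-assessed ORR loses a patient only when the first response is a CR and the next visit, before confirmation, is the affected one. Investigator PFS and DoR change only if the 8.4.1 note is carried into PFS. The primary ICR-based ORR changes only if ICR readers also record PR for such a visit, which is not shown. The futility analysis counts unconfirmed responses, so it is untouched.

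The size is small: fewer than one patient expected to lose responder status, and at most about 1.8 with a progression visit if the note reaches PFS. Both figures rest on assumed CR and NE rates. The case for acting is that the rule is contradictory and cheap to repair, not that it threatens the primary result.

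**What to change.** 1. In Protocol 8.4.1 and SAP Table 6, limit the rule that CR followed by PR is progression to visits where a previously cleared lesion is recorded as present again. Put that rule in Table 6 in place of the entry saying the scenario cannot occur.
2. In SAP 3.1.3 and 3.2.1, for investigator data, treat a post-CR visit with target CR, non-target NE and no new lesion as NE when deriving confirmation and progression. The existing CR, NE, CR rule then applies, and a later CR is still needed to confirm.
3. In SAP 3.2.2, state that such a visit is not a PFS or DoR event.
4. Align the Independent Review Charter with this. Do not override reader-supplied ICR visit responses by program.

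The cost is wording in the protocol and SAP, one programming condition and a note in the charter. No new data are needed. It should be settled before database lock, by which time Protocol 8.1 requires SAP amendments to be final.

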8.4.2 Secondary endpoints

Duration of response (DoR)

DoR will be defined as the time from the date of first documented response, (that is subsequently confirmed) until date of documented progression or death in the absence of disease progression. The date of the response start will be defined as the latest of the dates contributing towards the first visit response of PR or CR. If the response is not confirmed, it will not be included. The end of response should coincide with the date of progression or death from any cause used for the PFS endpoint. If a patient does not progress following a response, then their duration of response will use the PFS censoring time.

Disease control rate (DCR)

DCR is defined as the percentage of patients who have a best overall response of CR or PR or SD (at 6 months).

Progression free survival (PFS)

PFS is defined as the time from date of first dose until the date of objective disease progression or death (by any cause in the absence of progression) regardless of whether the patient withdraws from study therapy or receives another anti-cancer therapy prior to progression. Patients who have not progressed or died at the time of analysis will be censored at the time of the latest date of assessment from their last evaluable RECIST assessment. However, if the patient progresses or dies after three or more missed RECIST assessments visits, the patient will be censored at the time of the latest evaluable RECIST assessment. If the patient has no evaluable visits or does not have baseline data they will be censored at 0 days unless they die within two visits of baseline.

The PFS time will always be derived based on scan/assessment dates not visit dates. RECIST assessments/scans contributing towards a particular visit may be performed on different dates. The following rules will be applied:

- Date of progression will be determined based on the earliest of the dates of the component that triggered the progression
- When censoring a patient for PFS the patient will be censored at the latest of the dates contributing to a particular overall visit assessment.

Overall visit assessments will be determined for each assessment (scheduled or unscheduled) and will contribute to the derivation of PFS. Objective disease progression is defined as: at least a 20% increase in the sum of the diameters of the target lesions (compared with a previous minimum sum) and an absolute increase of >5 mm, an overall assessment of progression or a new lesion.

Overall survival (OS)

OS is defined as the time from the date of first dose until death due to any cause. Any patient not known to have died at the time of analysis will be censored based on the last recorded date on which the patient was known to be alive.

Note: Survival calls will be made in the 2 weeks following the date of the data cut-off for the primary analysis, and if patients are confirmed to be alive (or if the death date is post the relevant data cut-off date) these patients will be censored in the associated analyses at the date of the data cut off.

Time to discontinuation of IPs or death (TDT)

TDT is defined as the time from the date of first doses of IPs to the earlier of the date of discontinuation of both IPs, or death date. Both IPs should be discontinued at the same time but in rare circumstances discontinuation of one of the IPs before the other may be allowed (see Section 3.9). In such a case, TDT will reflect the time from the date of first dose to the earliest IP discontinuation date.

HRQoL Analyses:

The EORTC-QLQ-C30 and EORTC-QLQ-OV28 questionnaires will be used. Descriptive statistics of absolute scores and change from baseline of all subscales will be presented and plots will be generated as appropriate to interpret changes over time.

Proportions of patients who had improved, stayed the same or deteriorated for all subscales (symptom and functioning scales) will be presented. A 10 point change in score will be used as cut-off point. The quantity and impact of missing data will be evaluated. If warranted, some investigation of HRQoL data by whether patients are still taking study drug will be performed.

- Symptom Improvement Rate at 8 weeks
 - For dyspnea, pain and constipation from QLQ-C30 and abdominal/GI symptoms from QLQ-OV28, the symptom improvement rate at 8 weeks will be defined as the number (%) of patients showing a clinically meaningful improvement (a decrease from baseline score >10 ; Osoba et al 2005) in that symptom from baseline. The denominator will consist of a subset of the FAS population who have a baseline symptom score >10 .
